4. STUDY OBJECTIVE

The primary study objective is to compare the clinical outcomes of patients treated with the FlowTriever System versus Catheter-Directed Thrombolysis (CDT) for use in the treatment of acute pulmonary embolism (PE).

5. OUTCOME VARIABLES

PRIMARY ENDPOINT DEFINITION

The primary endpoint is a composite clinical endpoint constructed as a win ratio, a hierarchy of the following, which are assessed at hospital discharge or at 7 days after the index procedure, whichever is sooner:

1. All-cause mortality, or
2. Intracranial hemorrhage (ICH), or
3. Major bleeding per ISTH definition⁴, or
4. Clinical deterioration defined by hemodynamic or respiratory worsening, and/or escalation to a bailout therapy, or
5. ICU admission and ICU length-of-stay during the index hospitalization and following the index procedure.

Definition of Intracranial Hemorrhage

Intracranial hemorrhage (ICH) is defined as ANY bleeding involving the brain parenchyma, ventricular system, or subarachnoid, subdural, or epidural regions, as identified by CT scan or MRI, regardless of symptoms.

Definition of Major Bleeding

Major bleeding is defined according to the International Society for Thrombosis and Haemostasis (ISTH) definition of major bleeding in non-surgical subjects⁴.

1. Fatal bleeding, and/or
2. Symptomatic bleeding in a critical area or organ, such as intracranial, intraspinal, intraocular, retroperitoneal, intraarticular or pericardial, or intramuscular with compartment syndrome, and/or
3. Bleeding causing a fall in hemoglobin level of 2 g/dL (1.24 mmol/L) or more, or leading to transfusion of two or more units of whole blood or red cells.

Definitions of Clinical Deterioration and Bailout

Clinical deterioration is defined as documented objective hemodynamic or respiratory worsening that is new (i.e. not present at the time of enrollment).

Clinical deterioration is when one or more of the following is definitively documented, with relation to both the severity and the duration of the event:

- Hypotension with systolic blood pressure <90 mm Hg lasting at least 30 minutes, unresponsive to fluid resuscitation, and requiring the addition of or increased dose of vasopressors

- Fall in systolic blood pressure by 40 mm Hg or more, lasting at least 30 minutes, and accompanied end-organ hypoperfusion (such as oliguria, mental status changes, ischemic extremities)
- Cardiac arrest requiring cardiopulmonary resuscitation
- Bradycardia lasting more than 10 minutes, accompanied by hypotension, and requiring pharmacologic intervention or insertion of a pacemaker
- Ventricular tachycardia or fibrillation requiring pharmacologic intervention or defibrillation
- Requirement for an increase in fraction of inspired oxygen requirements 0.20 or greater, lasting longer than 30 minutes (e.g. from 0.21 to 0.41)
- Need for intubation in a previously non-intubated subject, or unplanned use of extracorporeal membrane oxygenation (ECMO)

Note that transient fluctuations in hemodynamic and/or respiratory function may be common during thrombectomy and thrombolysis procedures, and events not meeting both severity and duration requirements are not considered meeting the definition of Clinical Deterioration. Such changes may resolve spontaneously upon continuation of an existing treatment plan, and as such are unremarkable. Vagal episodes are also, in themselves, not considered Clinical Deterioration. Shorter term changes in hemodynamic or respiratory function, when accompanied by an unplanned escalation of therapeutic measures under the primary clinician's judgement to avoid overt deterioration, may be considered Bailout Therapy. Any such escalations of therapy will be documented in detail and adjudicated by a Clinical Events Committee (CEC).

Bailout Therapy is an unplanned escalation of therapeutic measures, taken when the patient's condition has not improved or is not improving according to expectations. Potential Bailout Therapy events will be adjudicated by a Clinical Events Committee, including when any of the following occur:

- Unplanned use of additional mechanical, pharmacomechanical, pharmacologic catheter-based therapies, or systemic thrombolytics, or changing from the assigned treatment strategy, after initial treatment strategy as assigned was initiated.
 - If catheter-directed thrombolysis (CDT) was the assigned treatment strategy and emergent/clinically driven systemic thrombolytic administration (e.g. ≥ 10 mg tPA) was required after CDT was initiated, this would be considered a bailout.
 - If the length of thrombolytic administration is simply extended and is not emergent or clinically driven, this would not qualify as a bailout.
 - If mechanical thrombectomy was the assigned treatment strategy, low-dose catheter-directed **adjunctive** thrombolytic therapy (less than 10 mg tPA) that is administered intra-procedurally or post-procedurally will be *strongly discouraged* but not considered a bailout
- Surgical thrombectomy

Before escalating to a Bailout Therapy, physicians are encouraged to consider the patient's condition and identify one or more reasons from the following list to justify the need for Bailout Therapy. These reason(s) will be documented in the study case report forms (CRFs).

- Persistent elevated respiratory rate
- Ongoing or increased requirement for supplemental oxygen
- Persistent or new-onset tachycardia
- Sustained or sudden bradycardia
- Sudden or persistent hypotension, not associated with a vagal episode, or signs of end-organ hypoperfusion
- Hemodynamic worsening or lack of hemodynamic improvement
- Lack of improved lung perfusion, or inadequate clot resolution
- New-onset, persistent, or worsening symptoms of PE

Any unplanned escalation of therapy adjudicated by the CEC to not meet clinical definitions for Bailout Therapies will be considered a protocol deviation.

Definition of ICU Admission and ICU Length of Stay

ICU Admission will be defined as admission or transfer to an Intensive Care Unit (ICU), Critical Care Unit (CCU), or similar high-acuity floor, collectively referred to as “ICU.” For the purpose of the endpoint assessment, ICU Admission is met under the following conditions:

- Orders are entered for Subject to be admitted or transferred to the ICU after the end of the Index Procedure and before hospital discharge from the index hospitalization, up to a maximum of 7 days from the end of the Index Procedure, or
- Subject had been in the ICU leading up to the Index Procedure, with plans to return to the ICU immediately after the end of the Index Procedure, with or without a transfer to a PACU, recovery room, or similar temporary step-down unit according to local standard.

ICU Length of Stay (LOS) is the total number of hours a subject is medically required to be in the ICU, measured from the end of the Index Procedure or the time of ICU Admission, whichever is later, until the time of an *order to discharge* the subject from the ICU or transfer the subject to a standard or lower-acuity unit. If a subject remains physically located in the ICU due to hospital bed availability, transport delays, or other non-medical reasons instead of a need for high acuity of care, the time of the order for discharge or transfer, rather than the actual time a subject physically leaves the ICU, is used for assessing ICU LOS.

For subjects getting discharged from or transferred off the ICU and returning again during the index hospitalization, up to a maximum of 7 days after the Index Procedure, the total hours of all ICU admissions or transfers during that period (i.e., after the Index Procedure and until hospital discharge up to a maximum of 7 days) are used for assessing ICU LOS.

Subjects who had been in the ICU leading up to the Index Procedure, but *not* returning to the ICU after the end of the Index Procedure, are *not* considered to have had an ICU Admission per the endpoint definition.

For the win ratio primary endpoint, ICU admission and ICU LOS are characterized hierarchically as follows:

1. No ICU Admission
2. ICU Admission, lasting between 0 – 24 hours
3. ICU Admission, lasting longer than 24 hours

SECONDARY ENDPOINTS

The secondary endpoints of the study will assess safety, effectiveness, and utility measures, as follows:

- Composite clinical endpoint constructed as a win ratio hierarchy of the following four components, assessed at hospital discharge or at 7 days after the index procedure, whichever is sooner:
 - All-cause mortality, or
 - Intracranial hemorrhage (ICH), or
 - Major bleeding per ISTH definition⁴, or
 - Clinical deterioration defined by hemodynamic or respiratory worsening, and/or escalation to a bailout therapy
- Individual components of the win ratio composite endpoint, assessed at hospital discharge or at 7 days after the index procedure, whichever is sooner:
 - All-cause mortality
 - Intracranial hemorrhage (ICH)

- Major bleeding per ISTH⁴ definition
- Clinical deterioration defined by hemodynamic or respiratory worsening, and/or escalation to a bailout therapy
- ICU admission and ICU length of stay during the index hospitalization and following the index procedure
- All-cause mortality within 30 days from index procedure
- PE-related and all-cause readmission within 30 days from index procedure
- Device and drug-related serious adverse events through the 30 day visit
- Clinically Relevant Non-Major (CRNM) and Minor bleeding events through hospital discharge or at 7 days after the index procedure, whichever is sooner
- Change in right-ventricular/left-ventricular (RV/LV) ratio from baseline to 24 hour visit, as measured by echocardiography or CT
- mMRC Dyspnea score at 24 hour visit and 30 day visit
- Length of total hospital stay and post-index-procedure hospital stay (to a maximum of 30 days)
- Disease-specific and general health-related quality of life at the 30 day visit (PEmb-QoL and EQ-5D-5L)

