The ULTIMA study compared EKOS to AC (heparin) alone in a total of 59 intermediate-risk PE patients across eight centers in Switzerland and Germany.⁴⁵ Results demonstrated a significantly greater reduction in RV/LV ratio, along with other echocardiographic right heart parameters, at 24 hours in EKOS patients compared to those treated with heparin. However, any significant difference in RV/LV ratios between EKOS and heparin was absent at 90 days.⁴⁵ There was no device-related mortality or major bleeding events related to either study treatment, but minor bleeding complications were observed in 10% and 3% of patients in the USAT and CDT arms, respectively ($P=0.61$).

The SEATTLE II study was a single-arm prospective study of 150 submassive and massive PE patients to further evaluate the safety and efficacy of EKOS, with a primary efficacy outcome of the change in RV/LV ratio within 48 hours of procedure initiation, and a primary safety outcome of major bleeding within 72 hours of procedure initiation. One hundred fifty submassive and massive PE patients each received 24mg of tPA, infused either in one catheter over 24hr, or in two catheters over 12 hours. Results demonstrated statistically significant improvements in RV/LV ratio, mean PAP, and thrombus burden as defined by the modified Miller Index score at 48 hours. One severe bleed and 16 moderate bleeding events in 15 patients (10%) occurred out to 72 hours.⁴⁶ Further refinement of the lytic dose and infusion duration using EKOS was conducted in the OPTALYSE PE trial, a multicenter, prospective study with 101 intermediate-risk PE patients randomized to 1 of 4 study arms in which both tPA dose and infusion duration were varied.⁴⁷ It is notable that randomization and enrollment into the study arm using 12mg (unilateral)-24mg (bilateral) of tPA over 6 hours was stopped after an ICH developed that was considered probably related to thrombolytic therapy and anticoagulation by the safety monitor. Results indicated that lower-dose tPA (as low as 4 mg per lung) and infusion duration as low as 2 hours was as effective as 6mg or 12mg doses infused up to 6 hours.

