The initial catheter-based intervention for acute PE is considered the Index Procedure. The procedure is conducted under fluoroscopic/angiographic guidance. Refer to the Instructions for Use (IFU) for techniques and methods for device deployment. The following assessments are collected during the index procedure including:

- Anticoagulation regimen
- Clinical labs (Hemoglobin, ACT, and PTT collected just prior to index procedure intervention)
- Oxygenation status collected just prior to index procedure
- Invasive PA pressures (**required** pre-index procedure)
 - Interventionalists will collect pulmonary artery pressures immediately before primary therapeutic catheter insertion.
- Invasive PA pressures (**optional** post-index procedure)
 - Trained interventionalists will collect pulmonary artery pressures at least 10 minutes after primary therapeutic catheter (for CDT) begins therapy, or after the primary therapeutic catheter (for FlowTriever) is removed for the last time. Additional PA pressures are requested to be collected in the CDT subjects 6 hours (\pm 2 hours) post procedure using the same technique.
- Bleeding measures
- Adverse event assessment

The Index Procedure begins when access for treatment is obtained. The Index Procedure is considered complete upon exit from the procedure room. The time of exit from the procedure room is the time reference used for the subsequent visit windows including the 24-hour visit. The 7-day maximum for in-hospital primary endpoint

assessment is defined as 168 hours from the end of the Index Procedure. The 30-day Visit window refers to 30 calendar days from the day the Index Procedure ends.

Recommendations for Anticoagulation Management and Thrombolytic Therapy

In order to approximate real-world practice, the use of pre-procedure, intra-procedure, and post-procedure anticoagulation should be guided by investigator discretion, local standard of care, and in accordance with IFU for the assigned therapy.

Similarly, dose and duration of thrombolytic agents in subjects assigned to CDT is guided by investigator discretion, local standard of care, and in accordance with IFU. Initial dosing strategy should be recorded in the corresponding CRF, along with any changes in dose throughout the infusion, including extended infusion times. Bolus thrombolytics that are part of initial treatment plan are not considered bailout, although bolus lytics are discouraged in subjects assigned to FlowTriever therapy.

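### The bailout definition exempts low-dose catheter lytic added after FlowTriever, with no matching exemption for mechanical therapy added after CDT, so tier 4 leans toward FlowTriever

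*Protocol*

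**What the plan says.** Tier 4 of the primary hierarchy, which is also the last tier of the four-component secondary composite, is "Clinical deterioration defined by hemodynamic or respiratory worsening, and/or escalation to a bailout therapy". The bailout list in Protocol section 5 (Definitions of Clinical Deterioration and Bailout, repeated in section 17) opens with a rule that names no arm: "Unplanned use of additional mechanical, pharmacomechanical, pharmacologic catheter-based therapies, or systemic thrombolytics, or changing from the assigned treatment strategy", once the assigned treatment has begun. These are candidates rather than automatic events: "Potential Bailout Therapy events will be adjudicated by a Clinical Events Committee".

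Sub-rules follow for each arm:

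- **FlowTriever:** adjunctive catheter-delivered "thrombolytic therapy (less than 10 mg tPA) that is administered intra-procedurally or post-procedurally will be" discouraged but not counted as a bailout.
- **CDT, counted:** "emergent/clinically driven systemic thrombolytic administration (e.g. ≥ 10 mg tPA) was required after CDT was initiated, this would be considered a bailout".
- **CDT, not counted:** "If the length of thrombolytic administration is simply extended and is not emergent or clinically driven, this would not qualify as a bailout".

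Protocol section 7 adds, without naming an arm: "Bolus thrombolytics that are part of initial treatment plan are not considered bailout". It advises against bolus lytic in the FlowTriever arm.

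No sub-rule exempts mechanical therapy added after CDT. SAP section 2.5 refers to the protocol for the definitions, and the only sensitivity analysis the SAP names (section 4) is multiple imputation.

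**The concern.** Each arm has one exemption for unplanned treatment, but the two differ in kind. The CDT exemption covers more of the assigned therapy. The FlowTriever exemption covers a limited amount of the other arm's therapy. Two subjects who each receive an unplanned add-on of the opposite modality can therefore be scored differently in tier 4, and the difference favours FlowTriever.

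The exempt amount cannot be dismissed as trivial on the protocol's own background. Section 3 reports from a dose-finding trial that "lower-dose tPA (as low as 4 mg per lung) and infusion duration as low as 2 hours was as effective" as larger doses. Two lungs at 4 mg make 8 mg, which lies below the exemption limit.

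Three features of the plan leave the gap open. CEC review applies the definition, so an asymmetry in the definition survives adjudication. The SAP describes the trial as open-label, so the operator who chooses the add-on knows the arm. The per-protocol analysis does not count these cases either: protocol deviations and receipt of other PE treatment are possible reasons for exclusion (SAP 3.2), so an exempt case may drop out, yet SAP 5.3 reads agreement between ITT and PP as support for the result.

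The results at stake are the primary Finkelstein-Schoenfeld (F-S) test, the four-component composite, and the one-sided Fisher test of tier 4 (SAP 5.4.6). SAP 5.6 classes the last two as safety endpoints at alpha 0.05 without multiplicity correction.

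**Working it through.** **1. The plan's own figure.** The required 432 subjects (216 per arm; 80% power, one-sided 2.5%) cannot be reproduced, because neither document gives component rates, the ICU split or a target win ratio (WR). The Yu-Ganju formula can be inverted instead:

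N = 4(1 + t)(1.960 + 0.842)² / [3 × 0.25 × (1 − t) × (ln WR)²], where t is the share of tied pairs.

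With N = 432 this gives WR 1.41 at t = 10%, 1.46 at 20%, 1.53 at 30% and 1.86 at 60%.

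**2. Add-on rate.** In FLARE, 106 − 104 = 2 subjects received lytics, and 2/106 = 1.9%. Dose is not given, so this is an upper bound on exempt use in that study. The rate of mechanical therapy after CDT is not documented. I take the same rate r in both arms.

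**3. Assumed rates, identical in both arms (true null).** Death 1%, ICH 0.5%, major bleeding 6%, other tier 4 events 3% or 5%, ICU none/≤24 h/>24 h 30/30/40%, components independent as in the plan's own simulation. Sample size is 275 per arm (550/2).

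**4. Worked case: r = 2%, other tier 4 events 3%, all FlowTriever add-ons exempt, all CDT add-ons counted.** Tier 4 is 3.00% in FlowTriever and 1 − 0.97 × 0.98 = 4.94% in CDT. Each row's wins and losses are weighted by the share of pairs still tied.

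| Tier | Pairs still tied | FlowTriever wins | FlowTriever losses |
|---|---|---|---|
| Death | 1 | 0.0099 | 0.0099 |
| ICH | 0.9802 | 0.0049 | 0.0049 |
| Major bleeding | 0.9705 | 0.0547 | 0.0547 |
| Tier 4 | 0.8610 | 0.8610 × 0.0494 × 0.97 = 0.0413 | 0.8610 × 0.03 × 0.9506 = 0.0246 |
| Sum of four | | 0.1108 | 0.0941 |
| ICU | 0.7952 | 0.7952 × 0.33 = 0.2624 | 0.2624 |
| Sum of five | | 0.3732 | 0.3565 |

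Four-component WR = 0.1108/0.0941 = 1.18. Primary WR = 0.3732/0.3565 = 1.05. The ICU tier decides most pairs and dilutes the tilt in the primary.

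**5. Rejection rates.** F-S figures come from 20,000 simulated trials per scenario at one-sided 0.025, using the protocol's variance. Fisher figures are exact. Ranges span other tier 4 events of 3% and 5%.

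| Scenario | Primary WR | Primary F-S | Four-component WR | Four-component F-S | Tier 4 Fisher at 0.025 | Fisher at 0.05 |
|---|---|---|---|---|---|---|
| No add-ons (tier 4 equal) | 1.00 | 0.024–0.025 | 1.00 | 0.024–0.027 | 0.014–0.016 | 0.029–0.035 |
| r = 1%, all exempt | 1.02 | 0.037 | 1.07–1.09 | 0.048–0.049 | 0.048–0.059 | 0.094–0.105 |
| r = 2%, half exempt | 1.02 | 0.035–0.036 | 1.07–1.08 | 0.047–0.049 | 0.045–0.054 | 0.089–0.100 |
| r = 2%, all exempt | 1.05 | 0.054–0.055 | 1.15–1.18 | 0.085–0.090 | 0.113–0.159 | 0.194–0.248 |

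At r = 5%, all exempt, the primary would reach WR 1.12 and rejection 0.14, but nothing in the documents points to a rate that high.

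**6. Scale.** In the worked case 0.7952 × 0.34 = 27% of pairs stay tied, so step 1 puts the design win ratio near 1.46 to 1.53. The tilt is ln 1.047/ln 1.53 = 0.046/0.425 = 0.11 to ln 1.047/ln 1.46 = 0.046/0.378 = 0.12 of that effect on the log scale.

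**The case against.** The strongest reply is that this is a disclosed, pre-specified and narrow carve-out. Much of that stands.

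- **Crossover charged to one arm only?** A reader might infer this, but the text does not support it. Catheter lytic at or above 10 mg, systemic lytic, other devices, surgery and a change of strategy can all still be adjudicated as bailout after FlowTriever.
- **A failed thrombectomy rescued with lytic never scores?** This also goes too far. The exemption is limited to adjunctive use, and documented clinical deterioration is a separate route into tier 4 whatever lytic was given. What remains open is that the protocol does not say where adjunctive use ends and a change of strategy begins.
- **A contradiction?** The exemption is nested under the general rule and reads as an exception to it, worded identically in sections 5 and 17. The criticism is that the exception is one-sided.
- **Is CDT also treated leniently?** Yes. Its exemption for a non-emergent longer infusion has no stated dose cap, and added mechanical therapy is only a potential bailout. But that leniency stays within the assigned modality, so it does not mirror the FlowTriever exemption.
- **Is the size speculative?** All event rates are assumed, and because this protocol discourages the add-on, use may fall below 1.9%. That limits how large the effect can be claimed to be. It does not remove the direction.

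**Conclusion.** The asymmetry is real and favours FlowTriever. It is confined to adjunctive catheter lytic below 10 mg tPA in subjects who do not otherwise meet tier 4 and whose pairs are not already decided by a higher tier.

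Near the one documented lytic rate, and with every FlowTriever add-on exempt, the effect on the primary is modest: enough to roughly double a one-sided 2.5% error, but only about a tenth of the effect the trial appears sized for. The four-component composite and the tier 4 Fisher test are more exposed, because no ICU tier dilutes them.

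These sizes depend on the assumed event rates, on equal add-on use in the two arms, on independence of components, and on the CEC counting every CDT add-on. They are a range of what could happen, not an estimate of bias in this trial. The point is worth acting on because it is cheap to settle. It does not by itself undermine the primary analysis.

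**What to change.** Three changes, all about how the endpoint is counted:

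1. Reconcile the general bailout rule with the FlowTriever exemption, so that it is clear how unplanned use of the other arm's modality is scored in each arm, including how the CEC separates adjunctive use from a change of strategy.
2. Report by arm the number of unplanned add-ons of the other modality, and how many were exempted.
3. Pre-specify in the SAP a sensitivity analysis of the primary F-S test and win ratio, the four-component composite and the tier 4 component, in which every unplanned use of the other arm's modality counts as tier 4 in both arms.

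The cost is some wording and one extra analysis. Unplanned escalations are already to be documented and sent to the CEC, so little or no new data collection is needed provided exempted lytic is captured there. The FlowTriever result may look less favourable. None of this bears on which dose or treatment a patient should receive.
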